## **APPENDIX 5. COLLECTION AND PROCESSING AND END-OF-TREATMENT BLOOD SAMPLES FOR BCR CLONOTYPING**

### Materials

- BD Vacutainer® Molecular Cell Preparation Tube, 8 mL (BD362761)
- DMSO (Sigma Cat. No D2650)
- IMDM- Iscove's Modified Dulbecco's Medium (Thermo Scientific Cat. No 12440-053)
- Fetal bovine serum- FBS (Thermo Scientific Cat. No 26140-079)
- HBSS- Hank's Balanced Salt Solution (Thermo Scientific Cat. No 14170-112)
- 2.0mL Cryo Storage Vial (VWR Cat. No 66008-728)
- 15mL Centrifuge Tubes (VWR Cat. No 21008-918)

### Procedure

#### **1. Blood Collection**

- 1.1. Collect whole blood in two (2) pre-labeled BD Vacutainer Molecular Cell Preparation Tubes (CPT), 8 mL each.
- 1.2. Invert each tube 8-10 times at store at room temperature (18-25°C).

#### **2. Shipping and Receiving blood samples in cell preparation tubes**

- 2.1. Sylvester sites will coordinate with the BioSpecimen Shared Resource (BSSR; [name] and [name]) for drop off/pick up of blood samples. *CPT processing should occur within 2 hours of collection.*
- 2.2. For non-Sylvester sites: Ship CPT tubes the same day via FedEx First Overnight to:  
ATTN: [name]  
SCCC Biospecimen Shared Resources  
[name]  
[name]

Samples should be kept and shipped at room temperature. Shipments should be sent Monday – Wednesday only to avoid being delayed in transit during the weekend.

[figure not shown]
#### **3. Freezing Medium Preparation (If necessary)**

- 3.1. Freezing medium consists of 70% FBS, 20% IMDM, and 10% DMSO.
- 3.2. To prepare 50mL of freezing medium
  - 3.2.1. Add 35mL FBS to a clean 50mL conical tube.
  - 3.2.2. Add 10mL IMDM to the conical tube and gently invert.
  - 3.2.3. Add 5mL DMSO to the conical tube, invert 5 times.
  - 3.2.4. Aliquot 5mL into 10-15mL conicals and store at -20° C until ready for use.

#### **4. CPT Processing**

- 4.1. Upon arrival, make sure that CPT tube is maintained in an upright position, and kept at room temperature until centrifugation.
- 4.2. For optimal results, processing should be started within 2 hours of blood collection; cell degradation will occur if tubes are stored for longer than four hours.

4.3. Centrifuge CPT tubes at 1800 x g for 40 minutes at room temperature. Turn the centrifuge brake off by setting the deceleration to zero.

4.4. After centrifugation, place the CPT tube in biological safety cabinet and carefully remove the top.

4.5. Using a sterile 5mL transfer pipet, gently pipette the plasma up and down against the gel plug to dislodge cells that are stuck to the top of the gel. Avoid vigorous pipetting that would disintegrate the gel plug itself.

4.6. Transfer the cell suspension from each CPT tube (2) from a single patient time point to a 15mL conical polypropylene tube. Bring cell suspension to a final volume of 12mL with HBSS.

4.7. Transfer one aliquot of cell suspension (1 million PBMC suspended in 1 ml RPMI with 10% bovine serum) into a tube for clinical flow (see below for procedure).

4.8. Centrifuge 15mL tubes at 250 x g for 10 minutes at room temperature.

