**STUDY SYNOPSIS**

Study Title	A Phase 2, open-label study of acalabrutinib in combination with R-ICE for relapsed or refractory non-germinal center diffuse large B cell lymphoma, transformed chronic lymphocytic leukemia/small lymphocytic leukemia or transformed marginal zone lymphoma
Protocol Number	20190706
Study Drug	ACALABRUTINIB (ACP-196), rituximab, ifosfamide, etoposide, carboplatin
Phase	2
Coordinating and Study Center	Sylvester Comprehensive Cancer Center
Additional Study Centers	
 
• Moffitt Cancer Center
 
• City of Hope
 

Study Objectives	
Primary Objective
 
 
• Improve complete remission (CR) rate of R-ICE for rel/ref non-GC DLBCL and transformed histologies from 29% to 50% with acalabrutinib + R-ICE for 3 cycles by RECIL.
 
 
Secondary Objectives
 
 
• Safety and tolerability of acalabrutinib with R-ICE in patients with rel/ref DLBCL
 
• (partial remission) PR, CR, overall response rate (ORR) of acalabrutinib + R-ICE
 
• Ability to mobilize <math>\geq 2 \times 10^6</math> CD34+ cells/kg
 
• Event-free survival (EFS), progression-free survival (PFS) and overall-survival (OS) at 1 year
 
 
Exploratory Objective
 
 
• Correlate efficacy endpoints (ORR, PFS, OS) with: baseline metabolic tumor volume (MTV), circulating cell-free tumor DNA (ctDNA), and the results of next-generation sequencing (NGS) of tumor. NGS in diagnostic biopsy if available.
 

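### Appendix 5 sends unprocessed cell tubes from the two outside centers overnight, beyond its own four-hour limit, so their exploratory BCR/MRD samples all fall outside the stated handling window

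*Combined protocol and SAP*

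**What the plan says.** Appendix 5 describes how blood for BCR clonotyping and MRD is handled before treatment and at end of treatment.

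- **Time limits.** Under CPT Processing, item 4.2 recommends a start within 2 hours for best results and then warns that "cell degradation will occur if tubes are stored for longer than four hours". Under Shipping and Receiving, item 2.1, which covers the Sylvester sites, adds "CPT processing should occur within 2 hours of collection".
- **Outside centers.** Item 2.2 reads "For non-Sylvester sites: Ship CPT tubes the same day via FedEx First Overnight to" the biospecimen resource at the coordinating center. It continues: "Samples should be kept and shipped at room temperature".
- **Where the tubes are spun.** Before shipping, the Blood Collection step lists only drawing the blood, inverting the tubes and holding them at room temperature. CPT Processing begins on arrival, where staff must "make sure that CPT tube is maintained in an upright position, and kept at room temperature until centrifugation".
- **Which centers.** The Study Synopsis lists one coordinating center, "Sylvester Comprehensive Cancer Center", and two additional centers.
- **What the cells are for.** Section 4.1.15 uses them for BCR clonotyping and for tracking low-frequency clones as MRD. It normalizes the MRD counts by flow cytometry, which Appendix 5 runs on an aliquot of the same cells.
- **Quality control.** Appendix 5 has the RNA integrity number (RIN) recorded, the RNA quantified and the library input fixed. It gives no RIN cut-off and does not ask for collection-to-processing time.

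**The concern.** The plan states a time after which the cells deteriorate, then gives two of its three centers a transport route that must exceed it. A site that follows item 2.2 exactly cannot meet item 4.2.

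What is at stake is the BCR/MRD result from those centers. Loss of cells or RNA could lower clone detection. At end of treatment, where the assay looks for rare clones, that could make a patient look MRD-negative when the clone was simply not recovered. The flow aliquot that normalizes the count comes from the same tubes, so numerator and normalizer share the fault.

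The delay also follows site: a target of about 2 hours at Sylvester, overnight everywhere else. A difference between centers in BCR/MRD results could not be told apart from a difference in handling. With no handling time recorded and no RNA threshold, the analysis could neither identify nor set aside the affected samples.

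**Working it through.** There is no planned figure to reproduce; the check compares elapsed time with the stated limit and then counts the patients affected.

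**1. Age of the tubes on arrival**

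Inputs from Appendix 5: recommended start within 2 hours, degradation after 4 hours, same-day dispatch by overnight courier, first centrifugation after arrival. The documents give no clock times. Assumed: draws between 08:00 and 18:00, delivery between 07:00 and 10:30 the next morning.

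Formula: hours from collection to arrival = (24 − draw hour) + delivery hour.

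| Draw | Delivery 07:00 | Delivery 10:30 |
|---|---|---|
| 08:00 | 16 + 7 = 23 h | 16 + 10.5 = 26.5 h |
| 12:00 | 12 + 7 = 19 h | 12 + 10.5 = 22.5 h |
| 18:00 | 6 + 7 = 13 h | 6 + 10.5 = 16.5 h |

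The range is 13 to 26.5 hours. Against the 4-hour limit: 13/4 = 3.3 and 26.5/4 = 6.6. Against the 2-hour recommendation: 13/2 = 6.5 and 26.5/2 = 13.3. The conclusion does not hinge on the clock times, since no schedule of same-day dispatch and next-morning delivery in this range comes near four hours.

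**2. Patients and samples affected**

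Inputs: 20 patients in stage 1 and 46 in total (Section 5.1); blood at two time points, pre-treatment and end of treatment (Appendix 1, footnote m). Accrual by site is not stated, so the outside centers' share is varied from one-third to two-thirds. The upper end is what equal accrual at three centers would give.

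| Outside share | Stops at 20 | Full 46 | Samples at 46 (× 2) |
|---|---|---|---|
| 1/3 | 6.7 | 15.3 | 31 of 92 |
| 1/2 | 10.0 | 23.0 | 46 of 92 |
| 2/3 | 13.3 | 30.7 | 61 of 92 |

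These are upper bounds for each share. Footnote m appears to limit the blood assessment to patients with an evaluable clonotype in the pre-treatment tumor, and not every patient will give both samples.

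**3. What depends on these cells**

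- BCR clonotyping and MRD (Section 4.1.15) and the flow normalization: exposed.
- ctDNA: not exposed. Appendix 5 collects it in separate tubes that may be held up to 10 days at 2 to 25°C.
- Tests in Section 5.2.7: these concern metabolic tumor volume, ctDNA and sequencing mutations. None is a BCR or MRD test.
- Primary complete-response endpoint: based on imaging and, where relevant, marrow. Not exposed.

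**The case against.** The strongest reply accepts the conflict in the text and disputes how much follows from it.

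- **The limits are soft.** The 2-hour figure is a recommendation, and in the shipping section it stands under the Sylvester item. The four-hour sentence is a warning, not an acceptance criterion. This stands, and the 2-hour figure should not be called a requirement. But the warning says that degradation will happen, and it is the only limit that the plan gives for these tubes.
- **Tumor tissue is the main baseline source.** Section 4.1.15 identifies the clonotype from the pre-treatment biopsy and treats blood as a supplement. This reduces the baseline risk. The end-of-treatment MRD sample has no such back-up.
- **Some controls exist.** A fixed RNA input offsets lower yield, though not fragmentation, and RIN is recorded. Without a cut-off, RIN does not decide which samples count.
- **Other material may settle it.** Section 4.1.15 refers to a laboratory manual, which is not part of these documents, and a figure in the shipping section is not shown. Either might describe a local spin before shipping. Appendix 5 would still need correcting, because as written it says otherwise.

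A reader might go further and infer that the BCR/MRD results are unreliable by design, or that correlations of MRD with response are biased through confounding by site. The documents support neither. They give no size for the loss of RNA or clones. They specify no test of BCR or MRD against response. Confounding of such a test would also need response to differ by center, which nothing in the plan shows; otherwise the likely effect is measurement error and lost sensitivity.

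**Conclusion.** The contradiction is real and lies within one appendix. As written, every CPT sample from the two additional centers falls outside the plan's own handling limit, at about 13 to 26.5 hours under the assumed clock times. That is roughly 15 to 31 of 46 patients if those centers enroll one-third to two-thirds, and about 7 to 13 of 20 if the trial stops after stage 1.

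The consequence is a possible loss of clone detection, some apparent MRD-negativity, and a handling delay that cannot be separated from site. How large that loss would be cannot be derived from the documents. It is confined to an exploratory assay and its normalization, so this is a minor point: worth correcting because it is cheap, not because it threatens the trial's main conclusion.

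**What to change.** 1. Reconcile the shipping and processing items of Appendix 5. State where and when tubes from the outside centers are processed and which time limit applies to them, and bring the laboratory manual into line.
2. Record collection-to-centrifugation time for every CPT sample.
3. State in advance an acceptance threshold for the RIN that is already being recorded.
4. Report BCR/MRD results by handling window and by site, with an analysis of in-window samples only as a sensitivity analysis. It should not be the main analysis: unless the shipping route changes, that restriction removes both outside centers and leaves a single-center result.

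The cost is one recorded time per sample, a threshold and a short addition to the analysis text, with some exploratory samples flagged or set aside. If the sponsor chooses processing at the outside centers, their laboratories take on extra work. The sample size and the primary analysis do not change.

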## 5. Cell Resuspension/Cryopreservation

- 5.1. When centrifugation is complete, aspirate the supernatant and gently flick the tube to break up the pellet.
- 5.2. Gently swirl cell suspension in 15mL tube and 1mL freezing media gradually.
- 5.3. Place the tube on ice and avoid any further mixing or agitation of the cells.
- 5.4. Using a sterile 5mL transfer pipet, transfer the cell suspension into a 2.0mL cryovial.
- 5.5. Place aliquots in a [name]™ freezing container filled with 100% isopropyl alcohol that has been pre-cooled at -80° C and return to -80 ° C. This will achieve a cooling rate of close to -1 ° C/minute.
- 5.6. Store samples at -80° C for 24 hours, then transfer to permanent storage in liquid nitrogen.
- 5.7. The BSSR will store plasma/mononuclear cell layer. When enough samples have been processed and stored to batch for RNA extraction, the BSSR will contact the Onco-Genomics Shared Resource (OGSR) to coordinate pickup of samples.
- 5.8. The OGSR will pick up samples on dry ice and process for RNA extraction (procedure below) immediately.

**RNA extraction and BCR clonotyping of pre-treatment and end-of-treatment blood samples****Materials**

- RNeasy Mini Kit 50 rxns (Qiagen 74104)
- Fragment Analyzer HS/SS RNA Kit
- Qubit HS/BR RNA Kit
- ArcherDx Immunoverse HS BCR IGH/K/L kit
- Fragment Analyzer HS DNA Kit
- Qubit HS DNA Kit
- MiSeq Reagents

**Procedure****1. RNA Extraction of isolated plasma/mononuclear cell layer following manufacturer's protocol.**

- 1.1. RNeasy Mini Kit (100 ug RNA) (Qiagen 74104)

**2. RNA Quantification and QC**

- 2.1. Run 2 ul of extracted total RNA on Fragment Analyzer using the High Sensitivity/Standard Sensitivity RNA Kit.
- 2.2. Visualize quality and record RIN score.
- 2.3. Run 2 ul of extracted total RNA on Qubit Fluorometer to determine concentration.

**3. Prepare sequencing library using the ArcherDx Immunoverse HS BCR IGH/K/L kit following the manufacturer's protocol.**

- 3.1. For pre-treatment samples, the input is 400 ng of RNA.
- 3.2. For end-of-treatment samples, the input is 1600 ng of RNA.

**4. Library Quantification and QC**

- 4.1. Run 2 ul of library on Fragment Analyzer using the High Sensitivity DNA kit.
- 4.2. Visualize quality of library and record average fragment size.
- 4.3. Run 2 ul of library on Qubit Fluorometer to determine concentration.

**5. Sequencing**

- 5.1. Libraries will be pooled and sequenced on an Illumina MiSeq (2x300 bp).
- 5.2. Pre-treatment libraries will be sequenced at 1 million read-pairs per sample.
- 5.3. Post-treatment libraries will be sequence at 4 million read-pairs per sample.

**6. Data Analysis**

**MRD assessment for normalization with blood samples****Procedure**

- 1) An aliquot from the plasma/mononuclear cell layer will be immediately transfer to Hematopathology by the Biospecimen Shared Resource.
- 2) Hematopathology will run clinical flow cytometry procedure.

**Collection of circulating cell free DNA (ccfDNA) of pre-treatment and end-of-treatment samples****Materials**

- PAXgene ccfDNA blood tube (PreAnalytix 768115)
- QIAamp MinElute ccfDNA Mini (Qiagen 55204)
- Fragment Analyzer HS DNA Kit
- Qubit HS DNA Kit

**Procedure****1. Pre-label two (2) PAXgene ccfDNA blood tubes (10mL) per patient.**

- 1.1. Collect whole blood in a PAXgene ccfDNA blood tube to its' maximum volume.
- 1.2. Invert tube 8 times to mix blood and additive.
- 1.3. Immediately store at 4°C. (*The whole blood sample can be stored for up to 10 days at temperatures from 2°C to 25°C, 7 days at up to 30°C, and 3 days at up to 37°C prior to processing. Do not store below 2°C*)

**2. Shipping and receiving blood samples in PAXgene tubes**

- 2.1. For Sylvester sites, collected samples will be received by the BSSR along with the above CPT blood tubes for plasma/mononuclear cells isolation.
- 2.2. For Non-Sylvester sites, ...
- 2.3. The BSSR will store the PAXgene ccfDNA blood tubes at 4°C.
- 2.4. Due to time restrictions on processing these tubes, the BSSR will contact the OGSR upon arrival and storage of samples to arrange retrieval.
- 2.5. The OGSR will receive the samples from the BSSR and store at 4°C until processing within the time frame based on sampling date and temperature storage.

**3. ccfDNA Isolation**

- 3.1. The whole blood sample will following the manufacturer's protocol for Plasma Preparation Isolation of ccfDNA in PAXgene ccfDNA blood tube prior to ccfDNA isolation.
- 3.2. ccfDNA Isolation will following the manufacturer's protocol
  - 3.2.1. QIAamp MinElute ccfDNA Mini (Qiagen 55204)

**4. ccfDNA Quantification and QC**

- 4.1. Run 2 ul of ccfDNA on Fragment Analyzer using the High Sensitivity DNA kit.
- 4.2. Visualize quality of ccfDNA.
- 4.3. Run 2 ul of ccfDNA on Qubit Fluorometer to determine concentration.

**5. The ccfDNA will be stored at -20°C.**
